9.4 ASSESSMENT OF AEs AND SAEs

Each AE must be assessed for seriousness, causality, severity and expectedness by the PI or another suitably qualified physician in the research team who is trained in recording and reporting AEs and who has been delegated this role.

The Chief Investigator (CI) may not downgrade an event that has been assessed by an Investigator as an SAE or SAR but can upgrade an AE to an SAE or SAR if appropriate.

The Investigator will make an assessment of seriousness (as defined in section 9.1).

9.4.1. Assessment of Causality

The Investigator will make an assessment of whether the AE is likely to be related to the study intervention according to the following definitions:

Unrelated: where an event is not considered to have occurred as a result of the study intervention.

Possibly Related: The nature of the event, the underlying medical condition, concomitant medication or temporal relationship make it possible that the AE has a causal relationship to the study intervention.

Where there are two assessments of causality (e.g. between PI and CI), the causality assessment by the Investigator cannot be downgraded. In the case of a difference of opinion, both assessments are recorded and the 'worst case' assessment is used for reporting purposes.

9.4.2. Assessment of Expectedness

If the AE is judged to be related to the study intervention, the Investigator will make an assessment of expectedness.

Expected: The type of event is expected in line with the study intervention.

Unexpected: The type of event was not listed in the protocol or related documents/literature as an expected occurrence.

9.4.3. Assessment of Severity

The Investigator will make an assessment of severity for each AE/SAE and record this on the CRF or SAE form according to one of the following categories:

Mild: an event that is easily tolerated by the participant, causing minimal discomfort and not interfering with every day activities.

Moderate: an event that is sufficiently discomforting to interfere with normal everyday activities.

Severe: an event that prevents normal everyday activities.

Note: the term 'severe', used to describe the intensity, should not be confused with 'serious' which is a regulatory definition based on participant/event outcome or action criteria. For example, a headache may be severe but not serious, while a minor stroke is serious but may not be severe.

9.5 REPORTING OF SAEs/SARs

Once the Investigator becomes aware that an SAE has occurred in a study participant, the information will be reported to the ACCORD Research Governance & QA Office **immediately or within 24 hours**. If the Investigator does not have all information regarding an SAE, they should not wait for this additional information before notifying ACCORD. The SAE report form can be updated when the additional information is received.

The SAE report will provide an assessment of causality and expectedness at the time of the initial report to ACCORD according to Sections 9.4.2, Assessment of Causality and 9.4.3, Assessment of Expectedness.

The SAE form will be transmitted by fax to ACCORD on **[name]** or may be transmitted by hand to the office or submitted via email to [contact]. Only forms in a pdf format will be accepted by ACCORD via email.

Where missing information has not been sent to ACCORD after an initial report, ACCORD will contact the investigator and request the missing information.

All reports faxed to ACCORD and any follow up information will be retained by the Investigator in the Investigator Site File (ISF).

9.6 FOLLOW UP PROCEDURES

After initially recording an AE or recording and reporting an SAE, the Investigator will follow each participant until resolution or death of the participant. Follow up information on an SAE will be reported to the ACCORD office.

AEs still present in participants at the last study visit will be monitored until resolution of the event or until no longer medically indicated.

10 TRIAL MANAGEMENT AND OVERSIGHT ARRANGEMENTS

The Edinburgh CTU will be responsible for trial management including: organisation of management group meetings, organisation of the steering committee and data monitoring committee, contracting with other organisations, preparation of REC and R&D applications, standard operating procedures, provision of the randomisation system, database development, data management, data analysis, writing the report and dissemination of findings.

10.1 TRIAL MANAGEMENT GROUP

The trial will be led by [name] and coordinated by an experienced ECTU trial manager and emergency medicine research nurse coordinator with support from ECTU. A project management group (PMG) comprising the applicants and relevant members of the ECTU team will be formed. The Academic and Clinical Central Office for Research & Development (ACCORD) in Edinburgh will provide Sponsorship and monitoring oversight for the project and the trial will be conducted in line with the relevant Sponsor SOPs which are <http://www.accord.ed.ac.uk/standardopprocs/CRSOPs.html>.

A Delegation Log will be prepared for each site, detailing the responsibilities of each member of staff working on the trial.

10.2 TRIAL STEERING COMMITTEE

A Trial Steering Committee (TSC) will be established to oversee the conduct and progress of the study. The terms of reference of the Trial Steering Committee, the draft template for reporting and the names and contact details are detailed in the TSC charter.

10.3 DATA MONITORING COMMITTEE

A Data Monitoring Committee will be composed of independent members and at a minimum will include a statistician, a cardiologist, a radiologist and an emergency or acute medicine physician. The Peto-Haybittle rule will be used by the Data Monitoring Committee as a guideline on the primary endpoint to trigger discussions on stopping the trial. Importantly the decision to stop the trial will not rely on p-values alone and will consider whether the results are convincing to the clinical community and patients.

10.4 INSPECTION OF RECORDS

Investigators and institutions involved in the study will permit trial related monitoring and audits on behalf of the sponsor and REC review. In the event of an audit or monitoring, the Investigator agrees to allow the representatives of the sponsor direct access to all study records and source documentation.

11 GOOD CLINICAL PRACTICE

11.1 ETHICAL CONDUCT

The study will be conducted in accordance with the principles of Good Clinical Practice (GCP).

A favorable ethical opinion will be obtained from the appropriate REC and local R&D approval will be obtained prior to commencement of the study.

11.2 INVESTIGATOR RESPONSIBILITIES

The PI is responsible for the overall conduct of the study at the site and compliance with the protocol and any protocol amendments. In accordance with the principles of GCP, the following areas listed in this section are also the responsibility of the PI. Responsibilities may be delegated to an appropriate member of study site staff.

11.2.1 Informed Consent

The Principal Investigator is responsible for ensuring informed consent is obtained before any protocol specific procedures are carried out and this process should be carried out as detailed in section 5.2 of the protocol.

11.2.2 Study Site Staff

The Investigator must be familiar with the intervention, protocol and the study requirements. It is the Investigator's responsibility to ensure that all staff assisting with the study are adequately informed about the intervention, protocol and their trial related duties.

11.2.3 Data Recording

The PI is responsible for the quality of the data recorded in the CRF at each Investigator Site. The source data plan identifies which source data correspond to CRF data and states which data are recorded directly into the CRF.

11.2.4 Investigator Documentation

Prior to beginning the study, each Investigator will be asked to provide particular essential documents to the ACCORD Research Governance & QA Office, including but not limited to:

- An original signed Investigator's Declaration (as part of the Clinical Trial Agreement documents);
- Curriculum vitae (CV) signed and dated by the Investigator indicating that it is accurate and current.

The ACCORD Research Governance & QA Office will ensure all other documents required by GCP are retained in a Trial Master File (TMF), where required, and that appropriate documentation is available in local ISFs.

11.2.5 GCP Training

Principal Investigators at each site should hold evidence of GCP training and ensure their staff are aware of the guidelines. All staff on the delegation log should have appropriate and relevant training in the research tasks that they undertake.

11.2.6 Confidentiality

All laboratory specimens, evaluation forms, reports, and other records must be identified in a manner designed to maintain participant confidentiality. All records must be kept in a secure storage area with limited access. Clinical information will not be released without the written permission of the participant. The Investigator and study site staff involved with this study may not disclose or use for any purpose other than performance of the study, any data, record, or other unpublished, confidential information disclosed to those individuals for the purpose of the study. Prior written agreement from the sponsor or its designee must be obtained for the disclosure of any said confidential information to other parties.

11.2.7 Data Protection

All Investigators and study site staff involved with this study must comply with the requirements of the Data Protection Act 1998 and General Data Protection Regulation (GDPR) with regard to the collection, storage, processing and disclosure of personal information and will uphold the Act's core principles. Access to collated participant data will be restricted to those clinicians treating the participants, representatives of the sponsor(s).

Computers used to collate the data will have limited access measures via user names and passwords.

Published results will not contain any personal data that could allow identification of individual participants.

12 STUDY CONDUCT RESPONSIBILITIES

12.1 PROTOCOL AMENDMENTS

Any changes in research activity, except those necessary to remove an apparent, immediate hazard to the participant in the case of an urgent safety measure, must be reviewed and approved by the Chief Investigator.

Amendments to the protocol must be submitted in writing to the appropriate REC and local R&D for approval prior to participants being enrolled into an amended protocol.

12.2 PROTOCOL VIOLATIONS AND DEVIATIONS

Prospective protocol deviations, i.e. protocol waivers, will not be approved by the sponsors and therefore will not be implemented, except where necessary to eliminate an immediate hazard to study participants. If this necessitates a subsequent protocol amendment, this should be submitted to the REC and local R&D for review and approval if appropriate.

Protocol deviations will be recorded in a protocol deviation log and logs will be submitted to the sponsors every 6 months. Each protocol violation will be reported to the sponsor within 3 days of becoming aware of the violation.

12.3 STUDY RECORD RETENTION

All study documentation will be kept for a minimum of 5 years from the protocol defined end of study point. When the minimum retention period has elapsed, study documentation will not be destroyed without permission from the sponsor.

12.4 END OF STUDY

The end of study is defined as 15 months after the recruitment of the last participant.

The Investigators and/or the trial steering committee and/or the co-sponsor(s) have the right at any time to terminate the study for clinical or administrative reasons.

The end of the study will be reported to the REC within 90 days, or 15 days if the study is terminated prematurely. The Investigators will inform participants of the premature study closure and ensure that the appropriate follow up is arranged for all participants involved.

A summary report of the study will be provided to the REC within 1 year of the end of the study.

12.5 INSURANCE AND INDEMNITY

The co-sponsors are responsible for ensuring proper provision has been made for insurance or indemnity to cover their liability and the liability of the Chief Investigator and staff.

The following arrangements are in place to fulfil the co-sponsors' responsibilities:

- The Protocol has been designed by the Chief Investigator and researchers employed by the University and collaborators. The University has insurance in place (which includes no-fault compensation) for negligent harm caused by poor protocol design by the Chief Investigator and researchers employed by the University.
- Sites participating in the study will be liable for clinical negligence and other negligent harm to individuals taking part in the study and covered by the duty of care owed to them by the sites concerned. The co-sponsors require individual sites participating in the study to arrange for their own insurance or indemnity in respect of these liabilities.
- Sites which are part of the United Kingdom's National Health Service will have the benefit of NHS Indemnity.

13 REPORTING, PUBLICATIONS AND NOTIFICATION OF RESULTS

The protocol for this trial will be submitted for publication and the trial results will be submitted for publication even if this trial stops early. If successfully completed the main paper from this project will be submitted for publication in a leading international general medical journal.

The main outputs will be provided to guideline developing bodies (including NICE, SIGN and the European Society of Cardiology), key professional organisations (such as the College of Emergency Medicine) and patient representative organisations (such as the British Heart Foundation).

13.1 AUTHORSHIP POLICY

Ownership of the data arising from this study resides with the study team. On completion of the study, the study data will be analysed and tabulated, and a study report will be prepared in accordance with the funders requirements. The authors for this project are listed in the trial's writing committee and publication policy document.

13.2 PUBLICATION

The clinical study report will be used for publication and presentation at scientific meetings. Investigators have the right to publish orally or in writing the results of the study.

Summaries of results will also be made available to Investigators for dissemination within their centres (where appropriate and according to their discretion).

13.3 PEER REVIEW

The trial has been reviewed by the Edinburgh Clinical Trials Unit executive group, the NIHR national cardiovascular group and HTA reviewers.

Appendix 1 - Management guideline for trial intervention arm

CTCA result	Troponin result	Trial treatment recommendation
Obstructive Disease: Stenosis $\geq 70\%$	Positive or Negative	1. ACS and secondary preventative therapies; 2. Invasive Coronary Angiography \pm revascularisation.
Moderate Non-obstructive Disease: Stenosis 50-69%	Positive	1. ACS and secondary preventative therapies; 2. Consider Invasive Coronary Angiography if uncertainty about the presence of obstructive coronary artery disease or functional testing.
Moderate Non-obstructive Disease: Stenosis 50-69%	Negative	1. Secondary preventative therapies; 2. Consider Invasive Coronary Angiography if uncertainty about the presence of obstructive coronary artery disease or functional testing.
Mild Non-obstructive Disease: Stenosis <50%	Positive	1. Consider ACS and secondary preventative therapies. 2. Consider alternative cause of chest pain and troponin rise
Mild Non-obstructive Disease: Stenosis <50%	Negative	1. Discharge with no further follow up; 2. Consider secondary preventative therapies.
Normal (no evidence of CAD)		Discharge with no further follow up.

SCOT-HEART	Trial acronym for 'Scottish Computed Tomography of the Heart' trial
SD	Standard Deviation
SOP	Standard operating procedure
SPO2	Peripheral capillary oxygen saturation
TNK/TPA	Tenecteplase/Tissue plasminogen activator
TSC	Trial Steering Committee
U	Units
Y/N	Yes/No

1. Introduction

This document details the criteria to be used for the definition of the analysis populations and the statistical methodology for analysis for the RAPID-CTCA trial, a randomised controlled trial of early computed tomography coronary angiography (CTCA) in patients presenting with suspected/confirmed acute coronary syndrome (ACS) to Emergency Departments (ED) and Medical Assessment Units.

This document has been compiled according to the Edinburgh Clinical Trials Unit (ECTU) standard operating procedure (SOP) "Statistical Analysis Plans" ECTU_ST_04 and has been written based on information contained in the study protocol version 7.0, dated 24 February 2020.

RAPID-CTCA is a multicentre, randomised, parallel-group open trial. Randomisation is at the individual level with a 1:1 allocation ratio, and is stratified by study site. Patients are randomised to either CTCA in addition to standard care or standard care alone. The aim was originally to recruit 2,500 patients in about 30 NHS tertiary and district hospitals (with or without on-site coronary angiography facilities) with emergency departments, acute medical, radiology, and cardiology services. This was updated to a size of at least 1735 in protocol version 7.

2. Statistical Methods section from the protocol

The trial will be reported on an intention-to-treat basis. The primary outcome is defined as first event of all cause death or subsequent non-fatal MI type 1 or 4b. Time to primary outcome is defined as time from randomisation to primary outcome. Patients discontinuing the study (for any reason) prior to reaching primary outcome will have their time to primary outcome censored at the last contact date. The relationship between intervention and the primary outcome will be analysed using Cox proportional hazard regression adjusted for study site (used to stratify the randomisation), baseline GRACE score, and previous CAD. The results will be expressed as a hazard ratio with the corresponding 95% confidence intervals and p-value. The individual elements of the composite primary outcome will be reported separately. Subgroup analysis on the primary outcome is planned for age, sex, baseline GRACE score, previous CAD, baseline ECG result, baseline troponin concentration, and presentation to a study site with or without on-site invasive coronary angiography facilities. These will be assessed by examining the effect of entering the treatment by subgroup interaction into the Cox regression model. Secondary outcomes will be analysed using appropriate methods: logistic regression for binary outcomes and linear regression for normally distributed continuous outcomes, adjusted as described above. Continuous outcomes that are not normally distributed will be analysed using appropriate nonparametric techniques. Every effort will be made to minimise missing data, and our primary analysis will be a complete case analysis. If there is a sufficient level of missing data for it to affect our conclusions, a multiple imputation analysis will be undertaken, using clinically appropriate variables, as a sensitivity analysis. Significance testing will use a hierarchical approach – for the primary outcome and the key secondary outcomes, statistical significance will be declared if the outcome in question, and all prior outcomes listed, have $p < 0.05$. P-values will be reported for all other outcomes but will not be declared to be significant. A full statistical analysis plan will be written during the trial and finalised prior to database lock.

3. Overall Statistical Principles

The intention-to-treat (ITT) population will include all patients who have been randomised into the RAPID-CTCA trial, and who did not withdraw consent for any of their data to be stored in the trial database. Patients will be analysed in the group to which they were allocated to, regardless of the

Statistical Analysis Plan	RAPID-CTCA
Version No	2.0
Date Finalised	19 Aug 2020

intervention they actually received. Analyses will be based on the ITT population, unless otherwise specified.

In general terms, categorical data will be presented using counts and percentages, whilst continuous variables will be presented using the mean, median, standard deviation (SD), minimum, maximum, lower and upper quartiles and number of patients with an observation (N). Data will be split by intervention group and time point where applicable.

All applicable statistical tests will be 2-sided and will be performed using a 5% significance level. 95% (2-sided) confidence intervals (CIs) will be presented. All analyses are testing superiority, rather than equivalence or non-inferiority. Significance testing will use a hierarchical approach – for the primary outcome and the key secondary outcomes, statistical significance will be declared if the outcome in question, and all prior outcomes listed, have $p < 0.05$. P-values will be reported for other outcomes but will not be declared to be significant.

Where there is missing data for an outcome variable, in the first instance, those records will be removed from any formal statistical analysis relating to that outcome variable (complete case analysis), unless otherwise specified. In tabulations, numbers of missing observations will be provided, but percentages will not include them.

Distributional assumptions underlying the statistical analyses will be assessed by visual inspection of residual plots. Normality will be examined by normal probability plots. If the distributional assumptions for the parametric approach are not satisfied, further data transformation (to alleviate substantial skewness (i.e. normalizing) or to stabilise the variance), or other suitable methods will be considered. This will be documented in the statistical results report together with the reasoning supporting the action taken, if applicable.

In general, analyses will be adjusted for study site (used to stratify the randomisation), baseline GRACE score (continuous), and previous CAD (yes/no), unless otherwise specified. Of note, study site will be included as a random effect (as there will be a large number of sites); whilst GRACE score, and previous CAD will be included as fixed effects. GRACE score will be adjusted for using a restricted cubic spline with 3 knots (thus using 2 degrees of freedom). The knots will be placed at the following percentiles of the predictor's marginal distribution: 0.1, 0.5, 0.9. Age is contained within GRACE score and will therefore not be adjusted for separately. Baseline GRACE score will be calculated from individual components, using the formula for predicting death or non-fatal MI within 6 months of admission with ACS [2], rather than using the GRACE score field in the database.

All analyses and data manipulations will be carried out using the most up to date version of SAS available [1].

4. List of Analyses

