Patients will be followed up using routine clinical notes and research contact with the patient by phone, email or post. A 3% loss to follow up (patient withdrawal and inability to retrieve data for the primary outcome from routine NHS records) is built into the sample size calculation for the primary outcome; all patients will be analysed for the primary outcome on an intention-to-treat basis. At Trusts where it is not possible to routinely get this data from the NHS records, the research team at site will attempt to contact the participant and/or their GP by telephone to gather the 12-month follow up data. All patients will be followed for 1 year.

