4.4 Primary outcome

The primary outcome will be all-cause death or subsequent non-fatal type 1 or type 4b MI at one year, measured as time from randomisation to first such event. MI will be defined according to the most recent Universal Definition [3] and will be adjudicated by two independent cardiologists blinded to the intervention. Patients discontinuing the study (for any reason) prior to reaching primary outcome

will have their time to primary outcome censored at the last contact date. The level of missing data is low, so a multiple imputation analysis for missing data is not necessary.

Primary analysis

If the proportional hazards assumption holds, using visual inspection, then the relationship between intervention and the primary outcome will be analysed using Cox proportional hazard regression. The results will be expressed as a hazard ratio with the corresponding 95% confidence intervals and p-value. The primary analysis will be adjusted as specified in the Overall Statistical Principles section of this document. An unadjusted analysis will also be presented, as a sensitivity analysis.

If the adjusted analysis p-value is <0.05 , this will be declared as a statistically significant p-value, and formal statistical testing will continue to the key secondary outcomes. If the adjusted p-value is not <0.05 , formal statistical testing of outcomes will stop at this point, and further p-values will be presented for information only.

The number of patients with an outcome event (by treatment group) will be tabulated, and the following statistics will be presented: adjusted HR (and 95% CI, p value), unadjusted HR (and 95% CI, p value). A Kaplan-Meier plot will be produced, showing results by allocated treatment - The p-value on the plot will be the p-value from the adjusted Cox regression analysis above..

A tabulated of the individual elements of the composite primary outcome will be produced – this table will specify whether each patient's primary outcome was death or MI.

Subgroup analysis

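### The adjusted primary Cox model has no rule for a missing GRACE component or previous CAD, so under the stated complete-case approach randomised patients with known outcomes would probably leave it

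*SAP*

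**What the plan says.** **The deciding model.** SAP 4.4 states: "The primary analysis will be adjusted as specified in the Overall Statistical Principles section of this document". The p-value from that adjusted model decides whether testing moves on to the key secondary outcomes, which SAP 4.5 adjusts in the same way.

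**Its covariates.** SAP section 3 adjusts for site (random effect), GRACE (restricted cubic spline) and previous CAD. On GRACE it says "Baseline GRACE score will be calculated from individual components", using a published formula for death or non-fatal MI within six months, "rather than using the GRACE score field in the database". It gives no instruction for a patient with a missing component.

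**Missing data.** SAP section 3: "Where there is missing data for an outcome variable, in the first instance, those records will be removed". That rule is limited to outcomes. SAP 4.4, in a paragraph on outcome definition and censoring, adds: "The level of missing data is low, so a multiple imputation analysis for missing data is not necessary". Protocol section 8, repeated in SAP section 2, describes the primary analysis as complete case, with multiple imputation as a conditional sensitivity analysis.

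**Who is to be analysed.** The SAP's ITT population is everyone randomised except those who withdrew consent for storage of their data, and it is the default for all analyses. Protocol 5.4.2 (Follow up) says "all patients will be analysed for the primary outcome on an intention-to-treat basis".

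**The companion analysis.** SAP 4.4: "An unadjusted analysis will also be presented, as a sensitivity analysis". It needs no GRACE value.

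**The concern.** A score built from several components is missing whenever any one of them is missing. Regression procedures normally omit a record with a missing covariate. Under a complete-case primary analysis, with imputation ruled out and no fallback named, a patient followed to one year could therefore drop out of the deciding model because one baseline reading was not recorded.

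Three things are at stake:

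- The analysis would carry the ITT label while containing fewer patients than the ITT population.
- Some events would be lost from the primary test, and again from each adjusted key secondary model.
- The adjusted and unadjusted hazard ratios would come from different patients, so a difference between them could not be put down to adjustment alone.

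**Working it through.** **Step 1. Does the plan's text lead to exclusion?** No sentence says that these patients are removed. The inference rests on three statements read together: the primary analysis is complete case (Protocol section 8; SAP section 2), multiple imputation is not to be done (SAP 4.4), and GRACE comes only from its components (SAP section 3). No alternative, such as a filled value, a missing category or a fallback score, appears anywhere. Exclusion is therefore the natural reading of the plan, though not an express instruction.

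**Step 2. Reproduce the plan's sample size.** Inputs from Protocol 4.1: overall event rate 6.8%, absolute risk reduction 3.4 percentage points, 80% power, two-sided 5%, at least 1720 patients. Allocation is 1:1 (SAP section 1). If 6.8% is the overall rate, the arms are 6.8% + 1.7% = 8.5% and 6.8% − 1.7% = 5.1%. This is a relative risk of 0.6, one of those that the protocol considered.

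n per arm = [1.960 × √(2 × 0.068 × 0.932) + 0.842 × √(0.085 × 0.915 + 0.051 × 0.949)]² / 0.034²

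= [0.6978 + 0.2990]² / 0.001156 ≈ 860, so 1720 in total.

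The stated figure reproduces. Expected events: 1720 × 0.068 = 117.

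**Step 3. Remove an assumed fraction m of patients.** The documents give no rate for m, so 1%, 2% and 5% are assumptions. With n = 860 × (1 − m):

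power = Φ{[0.034 × √n − 0.6978] / 0.3552}

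| Assumed m | Patients excluded | Events lost | Power | Total N to restore 80% |
|---|---|---|---|---|
| 0 | 0 | 0 | 80.0% | 1720 |
| 1% | 17 | 1.2 | 79.6% | 1738 |
| 2% | 34 | 2.3 | 79.2% | 1756 |
| 5% | 86 | 5.8 | 78.0% | 1811 |

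Over this range each 1% excluded costs about 0.4 percentage points of power.

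**Step 4. Cross-check on the time-to-event scale.** The implied hazard ratio is ln(1 − 0.051) / ln(1 − 0.085) = 0.589. Schoenfeld's approximation, Φ{√(events/4) × |ln HR| − 1.960}, gives 81.6% with 117 events, and 81.2%, 80.8% and 79.6% after 1%, 2% and 5% exclusion. The level differs slightly, but the losses are the same size.

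**Step 5. Is there any allowance for this loss?** Protocol 4.1 goes from 1720 to 1735 for loss to follow-up, which is 15 patients, or 15/1735 = 0.86%. Protocol 5.4.2 defines loss as withdrawal or primary-outcome data that cannot be retrieved. A missing covariate is neither, so nothing is set aside for it. (That 5.4.2 speaks of 3% is a separate matter.)

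**The case against.** The strongest reply is that the plan never says such patients are dropped, that missingness is likely to be rare, and that any loss would be visible. Much of this stands.

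- **No express exclusion.** A reader might infer that the plan orders every patient with an incomplete GRACE out of the model. It does not: the only explicit deletion rule concerns outcome variables. What remains is silence combined with a complete-case default.
- **No flat contradiction of intention to treat.** A reader might infer that the plan breaks its own promise. The protocol declares complete-case analysis alongside intention to treat, and the sentence in 5.4.2 itself allows for loss to follow-up. The SAP's ITT text mainly governs population and allocation. Tension is the right word.
- **Missingness is probably low.** Protocol 5.1 requires an ECG, vital signs, troponin and renal function as a minimum, renal function is an exclusion criterion, and baseline data are collected before randomisation. Against that, SAP 4.2 tabulates observations from the 60 minutes before randomisation, while patients may be approached up to 24 hours after presentation. The SAP does not say which readings feed GRACE.
- **A large loss is not supported.** The documents neither list the GRACE components nor give a missingness rate, so a figure built up from an assumed component count has no basis in them.
- **No bias between arms is shown.** The covariates are collected before allocation, so whether they are missing should not depend on arm.
- **Safeguards exist.** The unadjusted model keeps these patients, and SAP 4.1 reports the number analysed by arm. These disclose a loss but do not prevent it, and the unadjusted result does not control the testing hierarchy.

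**Conclusion.** The point holds as a gap in the handling of covariates. Followed as written, the plan would most naturally leave patients without a computable GRACE or a recorded previous CAD out of the adjusted primary and key secondary models. That fits poorly with the ITT population in SAP section 3 and with Protocol 5.4.2.

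The effect is probably small: between 1 and 6 of about 117 events, and 0.4 to 2 percentage points of power, if 1% to 5% of patients are affected. These figures rest on an assumed exclusion rate, on exclusions unrelated to risk, and on an unadjusted two-proportion approximation rather than the adjusted Cox model itself. The cost is precision and an inexact ITT label. It is worth correcting because it concerns the deciding test, leaves a choice to the analyst, and costs almost nothing to settle in advance.

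**What to change.** Add to SAP section 3:

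- If a GRACE component or previous CAD is missing, fill it with the pooled median (continuous) or mode (categorical) of that variable across both arms, using neither arm nor outcome. Calculate GRACE from the completed components, so that every ITT patient enters the adjusted models.
- Report the number of patients with a filled value, by arm and by variable.
- Give the model restricted to patients with complete covariates as a sensitivity analysis.

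Do not fall back on the database GRACE field. The SAP deliberately sets it aside, and the documents do not show that it uses the same formula, so a fallback could mix two scores in one spline.

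The cost is a short paragraph and a few lines of code. The small downside is that a few covariate values are approximate, which slightly weakens the adjustment for those patients. Because the filled value ignores arm and outcome, it does not favour either arm.
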